5.8 Safety Analysis

5.8.1 Exposure

5.8.1.1 Dose Intensity

Idasanutlin should be taken orally QD approximately the same time in Days 1 to 5 of each 28-day treatment cycle. Idasanutlin is administered orally. The standard dose is 150 mg (with possible intra-patient dose-escalation to 200 mg and dose reduction to 100 mg).

In summarizing dose intensity, a dose is considered to be missed if there is more than one day between two doses in a cycle. Dose intensity = number of doses actually received / expected number of doses during the protocol-specified treatment period (to be displayed as a percentage)

Idasanutlina summary of patients exposure by intensity category of <60; 60-80; >80%; Missing will be produced (DOSINT01) . Summary statistics (mean, s.d., median, range) will also be used to summarize the dose intensity.

An exposure summary table will be provided for all treated subjects (EXT01) as well as a listing (EXL01).

EXT01: Study Drug Exposure Table

Study Drug Exposure: <Specify Population>

Protocol: xxnnnnn

	Group 1 (N=nnn)
Treatment duration (dayst)	
n	nnn
Mean (SD)	xx.x (xx.x)
Median	xx.x
Min□max	xx□xx
Treatment duration (days)	
n	nnn
0□7	nn (xx.x%)
8□14	nn (xx.x%)
...	nn (xx.x%)
Dose intensity (%)	
n	nnn
Mean (SD)	xx.x (xx.x)
Median	xx.x
Min□max	xx□xx
Number of doses/cycles	
n	nnn
Mean (SD)	xx.x (xx.x)
Median	xx.x
Min□max	xx□xx
Total cumulative dose (unit)	
n	nnn
Mean (SD)	xx.x (xx.x)
Median	xx.x
Min□max	xx□xx
Missed doses	
n	nnn
At least one missed dose	nn (xx.x%)
Category 1	nn (xx.x%)
Category 2	nn (xx.x%)
...	nn (xx.x%)

- a) Treatment duration is the date of the last study drug administration minus the date of the first study drug administration plus one day. Dose intensity is number of doses actually received / expected number of doses during the protocol-specified treatment period (to be displayed as a percentage)

EXL01

Listing of Exposure to Study Drug <Analysis Population>

Protocol: xxnnnnn

Treatment: 25MG (N=8)

Center/ Patient ID	Visit	Study Day From	Study Day To	Dose	Unit	Frequency	Route
[REDACTED]	Day 1	1	27	25	MG	QD	ORAL
	Day 28	28	55	25	MG	QD	ORAL
	Day 1	1	27	25	MG	QD	ORAL
	Day 1	1	27	25	MG	QD	ORAL
	Day 28	28	55	50	MG	QD	ORAL
	Day 1	1	27	25	MG	QD	ORAL
	Day 28	28	55	25	MG	QD	ORAL
	Day 1	1	27	25	MG	QD	ORAL
	Day 28	28	55	25	MG	QD	ORAL

DOSINT01

Dose Intensity by Cycle and Category

	Dose Received* (% of Planned Dose)	B (N=XXX)	
		BENDAMUSTINE	
Cycle 1	<60	XXX	(XX.X%)
	60 - <80	XXX	(XX.X%)
	>=80	XXX	(XX.X%)
	Missing n	XXX	(XX.X%)
Cycle 2	<60	XXX	(XX.X%)
	60 - <80	XXX	(XX.X%)
	>=80	XXX	(XX.X%)
	Missing n	XXX	(XX.X%)

...
n represents the number of patients treated with obinutuzumab/bendamustine in the corresponding cycle.

* Percentages are calculated using the relative dose and are based on n.

DOSINT02

Dose Intensity by Cycle

Visit	Statistics	B (N=xxx)
		BENDAMUSTINE
Overall	n	xxx
	Mean (SD)	xx.x (xx.x)
	Median	xx.x
	Min - Max	xx.x - xx.x
Cycle 1	n	xxx
	Mean (SD)	xx.x (xx.x)
	Median	xx.x
	Min - Max	xx.x - xx.x

...
 n represents the number of patients treated with idasanutlin in the corresponding cycle.
 * Percentages are calculated using the relative dose and are based on n.

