6.1 TREATMENTS ADMINISTERED

Table 4 summarizes the treatments administered.

Table 4 Summary of Treatments Administered

Study Treatment Name:	Idasanutlin (RO5503781)
Dosage Formulation:	Film-coated tablets (containing spray-dried powder)
Unit Dose Strength(s)/Dosage Level(s):	50, 150, and 200 mg
Dose:	150 mg (with possible intra-patient dose-escalation to 200 mg; 100 mg in case of dose reduction)
Route of Administration:	Oral
Dosing Instructions:	
Idasanutlin should be taken orally QD in the morning on Days 1–5 of each 28-day treatment cycle. On days that PK sampling is required, study treatment dose scheduled for that day should be taken in the clinic to ensure accurate timing of the PK sampling. Idasanutlin should be taken at approximately the same time each day.
 
Idasanutlin is administered orally with or without food. Water may be taken as needed. If vomiting occurs within 15 minutes after taking idasanutlin and all expelled tablets are still intact, another dose should be given and the second dose should be noted in the drug diary. Otherwise no replacement dose should be given. Idasanutlin tablets should never be chewed, crushed, or broken before swallowing. For the QD regimen, if an idasanutlin dose is missed, it may be taken until noon. Otherwise, the dose should not be taken and dosing should be resumed with the next scheduled dose.

Packaging and Labeling:	Study treatment will be provided in high-density PE plastic bottles. Each bottle will be labeled as required per Roche standard and country requirement.

PK=pharmacokinetic; QD=once daily.

A drug diary will be provided to the patient to record oral administration of doses, including the date and time of dosing. Patients will be instructed to return empty bottles or unused tablets.

Guidelines for dosage modification and treatment interruption or discontinuation are provided in Section 6.6 or Section 7, respectively.

Please see the [Idasanutlin IB](#) for more details.

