5.8.1.2 Dose Modification

DOSMOD01

	ARM A (N=xxx)
Overall	
n	xxx
Number of patients with a dose modification	xx (xx%)
Type of modification	
n	xxx
Infusion Stopped and Restarted at the same rate	xx (xx%)
Infusion Stopped and Restarted at a lower rate	xx (xx%)
Prematurely Stopped and Not Restarted	xx (xx%)
Reason for modification	
n	xxx
Adverse Event	xx (xx%)
Other	xx (xx%)
xxxxxxxxxxxxxx	xx (xx%)
Cycle 1 Day 1	
n	xxx
Number of patients with a dose modification	xx (xx%)

...
 n is the number of patients who experienced a dose modification at the corresponding visit.

Listing 8 MEDL01

CRTN/Pt. No.	Clinical Planned Event	From	To	Durati on days hh:mm	TT be g da y	Actual Dose (mg)	Cumulat ive Dose (mg)	Treatmen t Modifica tion	Reason for Modific ation
xxxxxxx/xxx x									
BENDAMUS TINE	C1D1	ddmmmyyyy hh:mm:ss	ddmmmyyyy hh:mm:ss	x hh:mm	xx	xx.x	xx.x	xxxxxxxxx xx	xxxxxxxx xxx
	C2D1	ddmmmyyyy hh:mm:ss	ddmmmyyyy hh:mm:ss	x hh:mm	xx	xx.x	xx.x	xxxxxxxxx xx	xxxxxxxx xxx
	C3D1	ddmmmyyyy hh:mm:ss	ddmmmyyyy hh:mm:ss	x hh:mm	xx	xx.x	xx.x	xxxxxxxxx xx	xxxxxxxx xxx
	...								
OBINUTUZ UMAB	C1D1	ddmmmyyyy hh:mm:ss	ddmmmyyyy hh:mm:ss	x hh:mm	xx	xx.x	xx.x	xxxxxxxxx xx	xxxxxxxx xxx
	C1D8	ddmmmyyyy hh:mm:ss	ddmmmyyyy hh:mm:ss	x hh:mm	xx	xx.x	xx.x	xxxxxxxxx xx	xxxxxxxx xxx
	C1D15	ddmmmyyyy hh:mm:ss	ddmmmyyyy hh:mm:ss	x hh:mm	xx	xx.x	xx.x	xxxxxxxxx xx	xxxxxxxx xxx
	...								
...									

CRTN = Clinical Research Task Number (center no.).
 C = Cycle, D = Day.
 '?' = Duration could not be calculated.
 TT = Trial Treatment.

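### The SAP 5.8.1.1 missed-dose rule cannot see a five-day course that is cut short, and DOSMOD01 has no row for a change of tablet dose

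*SAP*

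**What the plan says.** **Regimen.** Protocol 6.1 (Table 4): "Idasanutlin should be taken orally QD in the morning on Days 1–5 of each 28-day treatment cycle". SAP 5.8.1.1 repeats it: "Idasanutlin should be taken orally QD approximately the same time in Days 1 to 5 of each 28-day treatment cycle". It also gives the dose levels: "The standard dose is 150 mg (with possible intra-patient dose-escalation to 200 mg and dose reduction to 100 mg".

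**Missed doses.** SAP 5.8.1.1 has one rule: "a dose is considered to be missed if there is more than one day between two doses in a cycle". The EXT01 shell has a row "At least one missed dose", and the categories beneath it are unfilled. Protocol Table 4 uses the word differently: there, a missed dose is a scheduled dose that was not taken.

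**Dose intensity.** The next sentence of SAP 5.8.1.1 reads "Dose intensity = number of doses actually received / expected number of doses during the protocol-specified treatment period". EXT01 reports it overall; DOSINT01 and DOSINT02 report it by cycle.

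**Dose modification.** SAP 5.8.1.2 consists of the DOSMOD01 shell and a listing (MEDL01). The shell counts patients with any modification, with reason, and splits by type. The types are "Infusion Stopped and Restarted at the same rate", "Infusion Stopped and Restarted at a lower rate" and a third row for treatment stopped early and not resumed.

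**Related definitions.** SAP 4.1.4 starts each cycle on the day of its first administration. SAP 4.3 defines a valid dosing record as one with a complete start date and an actual dose above zero.

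**The concern.** A rule that needs two doses with a gap between them cannot register doses missing from the end of a course. A patient who stops partway through the five days, for vomiting or a toxicity hold for example, has no later dose in that cycle to form the gap. Protocol 8.3.9.1 says gastrointestinal toxicity often starts within hours of dosing, and 6.1.1 says nausea and vomiting have led to discontinuation in other idasanutlin studies. A truncated course is therefore foreseeable, and it is the kind that the missed-dose row omits.

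The second gap concerns dose level. The protocol provides for escalation to 200 mg (4.1.2, 6.6), reduction to 150 or 100 mg (Tables 6 and 8) and an optional reduction to 100 mg after Cycle 13, the last expressly to learn about longer-term tolerability (6.6). A reader of the report will want to know how many patients had each change. The table named for dose modification has no row for any of them.

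**Working it through.** The plan gives no figure to reproduce, so the check is an enumeration.

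**Inputs.** Five planned doses per cycle (Protocol 6.1, SAP 5.8.1.1). The first dose defines cycle Day 1 (SAP 4.1.4). Every started cycle therefore includes Day 1, and each of the other four days is dosed or not.

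**Number of patterns.** 2^4 = 16, less the complete course, leaves 15 incomplete patterns.

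**Two readings of the rule.**
- Reading A: flag if two consecutive dose dates differ by more than 1.
- Reading B: flag if more than one dose-free day lies between them, that is, if the dates differ by more than 2.

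| Days dosed | A | B | Patterns |
|---|---|---|---|
| 1; 1-2; 1-2-3; 1-2-3-4 | not flagged | not flagged | 4 |
| 1,3; 1,2,4; 1,3,4; 1,3,5; 1,2,3,5; 1,2,4,5; 1,3,4,5 | flagged | not flagged | 7 |
| 1,4; 1,5; 1,2,5; 1,4,5 | flagged | flagged | 4 |

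- Unflagged under A: 4 of 15, exactly the truncated courses.
- Unflagged under B: 4 + 7 = 11 of 15. A single skipped day in mid-course is then not a missed dose either.

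**Dose intensity of the truncated courses.** With five doses expected per started cycle: 1/5 = 20%, 2/5 = 40%, 3/5 = 60%, 4/5 = 80%.

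**Disagreement inside EXT01.** Eight cycles to Week 32 give 8 × 5 = 40 planned doses. One course stopped after Day 3 gives 38/40 = 95% intensity and no missed dose. If all eight stopped after Day 3, intensity is 24/40 = 60% and there is still no missed dose. These are illustrations, not forecasts.

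**Dose level.** Intensity counts doses, so a full cycle at 100, 150 or 200 mg scores 5/5 = 100% each time. Measured in mg against 150 mg, the same cycles would be 500/750 = 66.7%, 100% and 1000/750 = 133.3%. The DOSINT01 and DOSINT02 footnotes speak of a relative dose but do not define it.

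**DOSMOD01 types.** Two of three are worded for infusions; the third can hold a course that was stopped. None of the three describes a dose-level change.

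**The case against.** The strongest reply is that the shortfall is visible elsewhere. Dose intensity falls for every truncated course and is tabulated by cycle, and EXT01 also gives number of doses and cumulative dose. The exposure summaries promised in Protocol 9.4.3 are duration, cycles started and cumulative dose, all of which EXT01 delivers; the missed-dose row is an SAP addition. The shells are plainly adapted from other studies (bendamustine and obinutuzumab labels remain), and the List of Planned Outputs, the reference for the full set, is not in the documents.

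Much of that stands, and it rules out several stronger readings that a reader might infer:
- *That truncated courses are reported as complete, so that tolerability as a whole looks better than it was.* Only the missed-dose row is wrong; intensity shows the deficit.
- *That late starts escape the rule, so that 14 of 30 incomplete patterns go unflagged (25 of 30 under Reading B).* Those counts include the 15 patterns without Day 1. Under SAP 4.1.4 a late first dose moves the cycle start, so they do not arise.
- *That the report contains no information on dose changes.* DOSMOD01 counts any modification with its reason. EXL01 and MEDL01 list doses, AE listings code doses increased or reduced, and AET01_02 counts patients with an AE leading to dose modification or interruption.

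The template argument does not dispose of the point. The missed-dose rule is SAP prose, not leftover shell text. SAP section 1 says that the specifications are detailed enough to program from, and 5.8.1.2 does not say that its rows will be replaced. Listings are not counts, and AE-linked outputs do not cover an escalation made for lack of hematocrit control or the optional reduction after Cycle 13.

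**Conclusion.** The missed-dose rule is wrong as written. It yields no missed dose for any of the four truncated courses under either reading, so EXT01 understates incomplete courses and can contradict its own intensity row. The size is 4 of 15 possible patterns under Reading A and 11 of 15 under Reading B. These are counts of patterns, each given equal weight. The documents give no frequencies, so the effect on the reported percentage of patients cannot be estimated.

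DOSMOD01 leaves a narrower gap: no specified summary table counts patients raised to 200 mg or lowered to 150 or 100 mg, although the information can be recovered from listings and, for AE-related changes, from AE outputs.

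The conclusion assumes that SAP 4.1.4 governs cycle starts, that five doses are expected per started cycle, and that the unseen output list does not redefine either item. No efficacy endpoint or decision rule uses these rows, and all analyses are descriptive.

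**What to change.** 1. In SAP 5.8.1.1, define missed doses for each started cycle as 5 minus the number of days with a valid dose (SAP 4.3). Count days, not tablets, so that a replacement after vomiting is not an extra day.
2. In DOSMOD01, replace the two infusion rows with dose increased, dose reduced, and cycle delayed or interrupted, each with its reason. Keep the row for treatment stopped and not resumed. Showing the dose level reached would let readers separate 200, 150 and 100 mg.
3. While the section is open, state whether intensity is by dose count or by mg, and reconcile the category boundary. A 4-of-5 course (80%) falls in the 60-80 band of the text but in the top band of the DOSINT01 shell.

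The cost is one reworded rule and one reprogrammed shell, plus the short clarification in item 3. The data are already collected in the drug diary and the study treatment eCRF. The reported missed-dose rate will be higher, and a dose whose record has an incomplete date will count as missed, because SAP 4.3 does not impute such dates; a footnote should say so.

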4.1.1 Length of the Study

The total duration of the study for each patient will be up to 112 weeks divided as follows:

- Screening Period: up to 28 days (4 weeks)
- Treatment Period: Day 1 Cycle 1 continues with repeating treatment cycles of 28 days until patients discontinue study treatment or at end of study (EOS; defined as 2 years [104 weeks] post initial dose).
- Safety follow-up: until 28 days (4 weeks) after the last dose of study treatment or until initiation of another anti-cancer therapy, whichever occurs first (see Section 1.2 for safety assessments at follow up).

Patients will be asked to return to the clinic 28 days (± 7 -day window) after the last dose of study medication to complete Final Visit assessments. In the event that the decision to withdraw from the study occurs after 28 days from the last dose of idasanutlin, e.g., due to interruption of intended cycle continuation due to an AE, then the Final Visit should occur on or as close as possible to the date of withdrawal. The visit at which a response assessment shows *no response* (NR) or PD may be used as the Final Visit if treatment is discontinued.

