4.1.5 Treatment period

Treatment period is defined as the time between Cycle 1 Day 1 and date of the clinical cutoff or the date of withdrawal or end of study, whichever comes first.

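### SAP dose intensity counts doses, so 100, 150 and 200 mg cycles all score 100%, while the DOSINT01/02 shells for the same measure use relative dose

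*SAP*

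**What the plan says.** SAP 5.8.1.1 sets out the schedule ("Idasanutlin should be taken orally QD approximately the same time in Days 1 to 5 of each 28-day treatment cycle") and the dose levels: "The standard dose is 150 mg (with possible intra-patient dose-escalation to 200 mg and dose reduction to 100 mg". It then gives the formula: "Dose intensity = number of doses actually received / expected number of doses during the protocol-specified treatment period". The footnote to the exposure table EXT01 repeats it: "Dose intensity is number of doses actually received / expected number of doses during the protocol-specified treatment period". Neither statement contains a mg term. The text assigns the resulting categories (<60; 60-80; >80%; missing) to table DOSINT01.

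The DOSINT01 shell heads its column "Dose Received* (% of Planned Dose" and uses the categories <60, 60 - <80 and >=80. The footnote to DOSINT01 and DOSINT02 reads "Percentages are calculated using the relative dose and are based on n".

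Two definitions of the treatment period bear on the denominator. Protocol 4.1.1 has "repeating treatment cycles of 28 days until patients discontinue study treatment or at end of study", the latter at 104 weeks. SAP 4.1.5 says "Treatment period is defined as the time between Cycle 1 Day 1 and date of the clinical cutoff or the date of withdrawal"; study completion is a third possible endpoint, and the earliest of the three applies.

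**The concern.** Reductions to 100 mg are part of this protocol: they appear in the treatment summary (Table 4), the dosing-delay guidance (Table 6), the diarrhea and hematologic toxicity guidance (Tables 7 and 8), and as an option after Cycle 13 (Section 6.6). Escalation to 200 mg is also allowed. A dose-intensity figure that cannot tell these levels apart is easily misread, because a reader of EXT01 will take 100% to mean the standard dose was delivered.

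The SAP also gives two rules for one output. A programmer who follows the text and one who follows the shell would produce different DOSINT01 tables, and the overall figures in EXT01 and DOSINT02 could differ under the same name. SAP 5 says the specifications should be detailed enough to be programmed correctly; on this measure they are not.

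**Working it through.** The plan states no numerical dose intensity, so there is no figure to reproduce. The check applies each rule to the same patients.

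**Inputs.** Five doses per 28-day cycle; standard dose 150 mg; other levels 100 and 200 mg (SAP 5.8.1.1). Two years = 104 weeks / 4 = 26 cycles = 130 doses, assuming no delays (Protocol 4.1.1).

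**Formulas.**
- Count rule (text, EXT01): doses received / doses expected.
- Mg rule (one reading of relative dose in DOSINT01/02): mg received / (doses expected × 150 mg).

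| All scheduled doses taken | Count rule | Mg rule |
|---|---|---|
| One cycle at 100 mg | 5/5 = 100% | 500/750 = 66.7% |
| One cycle at 200 mg | 5/5 = 100% | 1,000/750 = 133.3% |
| 26 cycles, 100 mg from Cycle 2 | 130/130 = 100% | 13,250/19,500 = 67.9% |
| 26 cycles, 100 mg after Cycle 13 | 130/130 = 100% | 16,250/19,500 = 83.3% |
| 26 cycles, 200 mg from Cycle 4 | 130/130 = 100% | 25,250/19,500 = 129.5% |

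**Categories.** The single 100 mg cycle is in the top category by count and in the 60 to 80 category by mg. At 150 mg, one missed dose in a cycle gives 4/5 = 600/750 = 80% under either rule. The text puts that cycle in the middle category and the shell puts it in the top one. With five doses per cycle, 80% is therefore an ordinary value.

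**Denominator.** A patient who stops after eight complete cycles scores 40/40 = 100% if the period ends at treatment discontinuation (Protocol 4.1.1). Under SAP 4.1.5 the period runs to withdrawal. If withdrawal is dated between the end of Cycle 8 and one cycle later, the range is 40/45 = 88.9% to 100%. After three complete cycles the corresponding figures are 100%, and 15/20 = 75% to 100%. The formula does not say which definition it uses.

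**Breaks.** Protocol 6.6 allows treatment breaks from the end of Cycle 13. For an illustrative break of six cycles within two years, the count rule gives 100/130 = 76.9% if break cycles carry expected doses and 100/100 = 100% if they do not. The SAP does not say which.

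**The case against.** The strongest reply is that reductions remain visible elsewhere. EXT01 has rows for total cumulative dose and for missed doses. EXL01 lists dose by visit, and MEDL01 lists actual and cumulative mg. DOSINT01/02, read as relative dose, could show a 100 mg cycle as 67%. DOSMOD01 counts patients with dose modifications, and the safety summary AET01_02 counts patients with adverse events leading to modification or interruption. Protocol 9.4.3 summarizes exposure by duration, cycles started and cumulative dose and does not name dose intensity. No hypothesis is tested. Most of this stands, and it limits the consequence.

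These outputs do not replace a clear intensity figure. Cumulative dose mixes level with duration: 26 cycles reduced from Cycle 2 total 13,250 mg, close to 18 cycles at the standard dose (18 × 750 = 13,500 mg). The type rows in DOSMOD01 describe infusions being stopped and restarted, with no row for a tablet dose reduction. The DOSINT shells still carry other products' names, so their footnote may be a template remnant. That leaves it less clear which rule governs.

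It can also be argued that the reference dose is a choice: against 150 mg, the optional reduction after Cycle 13 reads as a shortfall. That is fair, and it is a reason to state the reference dose explicitly.

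A reader might infer that the formula divides by the full two years, so that a compliant patient who stops after Cycle 8 scores 40/130 = 30.8%. The documents do not support this. Neither treatment-period definition fixes the denominator at 104 weeks, and both allow the period to end early.

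**Conclusion.** The point holds as an internal conflict and a misleading definition. By the written formula, complete cycles at 100, 150 and 200 mg all score 100%; in mg against the standard dose they are 66.7%, 100% and 133.3%. The shells for the same measure imply a different calculation, and the category limits disagree at exactly 80%. The denominator is ambiguous between two definitions, but this does not show that early discontinuation appears as low intensity.

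The mg percentages rest on 150 mg as the reference dose, and the two-year examples assume no delays. The effect is confined to descriptive exposure reporting. A reader might go further and treat dose intensity as the trial's main tolerability summary, or as an input to exposure-response work. The documents support neither: Protocol 9.4.3 bases safety on adverse events, laboratory tests, vital signs and ECGs, and the exposure-response analyses use PK data (Protocol Table 3 and 9.4.4).

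**What to change.** - Replace the formula in SAP 5.8.1.1, the EXT01 footnote and DOSINT01/02 with one relative dose intensity: mg received / (150 mg × 5 × cycles started), per cycle and overall.
- State that the reference is the standard dose, so escalation reads above 100% and any reduction, including the optional one after Cycle 13, reads below. This is a reporting convention only.
- State whether Protocol 4.1.1 or SAP 4.1.5 defines the treatment period for this measure.
- State how delays and breaks count. SAP 4.1.4 ends a cycle the day before the next one starts, so a denominator in cycles started does not register delay, and a cycle skipped during a break does not enter it.
- Use one set of category limits in the text and the shell.
- Keep the existing missed-doses row in EXT01, which carries the information that the count formula was giving.

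The cost is one formula plus edits to footnotes and shells. The mg data are already planned for listing in EXL01 and MEDL01, so no new data collection is needed. Some reported intensities will move below 100% and some above.
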